7.2 General Study Procedures

7.2.1 Screening Period

Informed consent must be obtained before completing any other screening procedure or discontinuation of standard therapy for any disallowed therapy. After signing the written informed consent form, sites will register the subject in IVRS/IWRS and screen the subject in order to assess eligibility for participation. The screening window is 14 days. If a subject has not met all eligibility criteria at the end of the 14-day window, the subject will be registered as a screen fail. Screen fail subjects may be eligible for re-screening one time.

7.2.2 Re-screening

Subjects who are unable to complete or meet eligibility on initial screening will be permitted to re-screen once. Re-screen subjects must first be registered as screen failed in IVRS/IWRS and subsequently registered as re-screened. Subjects will retain the same subject identification number assigned at the original screening. Once the subject is registered as re-screened, a new 14-day screening window will begin. If the re-screening period begins more than 14 days after the original signing of the informed consent form, all screening procedures, including informed consent must be repeated. If the re-screening occurs less than 14 days after the original signing of the informed consent, then only those criteria that were originally failed are required to be repeated. The PPD test, chest x-ray, and Quantiferon will not need to be repeated for re-screen subjects if negative at the original screening. However, subjects screen-failing for and not meeting the tuberculosis testing inclusion criterion are not permitted to rescreen.

7.2.3 Treatment Period

Visits will occur per the Schedule of Assessments during the treatment period from screening through week 2. Study visits may be completed within \pm 3 days of the target visit date. Prior to enrollment, subject eligibility must be confirmed with screening procedures. Subjects satisfying eligibility requirements will be enrolled. The date of the first dose of investigational product is defined as day 1. All subsequent doses and study visits will be scheduled based on the day 1 date.

The procedures completed during the 2-week treatment period are those listed in **Table 1**. Etanercept is to be administered after all assessments have been done for all visits with the exception of the VAS subject injection site pain assessment.

7.2.4 Safety Follow-up/End-of-Study

Thirty days (+ 7 days) after their last dose of etanercept, subjects will be contacted by phone by the study staff to follow-up on any continuing serious adverse events and inquire about the emergence of any new serious adverse events.

7.3 Description of Study Procedures

The sections below provide a description of the individual study procedures for required timepoints.

7.3.1 Informed Consent

All subjects must sign and personally date the IRB/IEC approved informed consent before any study-specific procedures are performed.

7.3.2 Demographic Data

Demographic data collection including sex, age, race, and ethnicity will be collected in order to study their possible association with subject safety and treatment effectiveness.

7.3.3 Medical History

The investigator or designee will collect a complete medical history from 5 years before enrollment through the first dose of etanercept, which will be recorded in the medical history CRF. Medical history will include information on the subject's concurrent medical conditions. Diagnosis dates for RA or PsA will also be collected.

7.3.4 Medication History

A complete history of RA or PsA medications starting at the time of diagnosis and up to screening will be recorded on the CRF. This information will include medication name, indication, dose, unit, frequency, route, start date and stop date. All other medications taken within 3 months before screening will be collected, including medication name, indication, dose, unit, frequency, route, start date and stop date.

7.3.5 Physical Examination

The screening physical examination will be a complete physical examination. Breast, genital, and rectal examinations are not required at any study visit unless specific evaluation is warranted. Physical examination findings at screening should be recorded in the medical and surgical history CRF.

The physical examination at subsequent study visits will consist of a musculoskeletal examination for RA and PsA subjects along with a skin examination for PsA subjects per standard of care. Examination findings should be recorded on the appropriate CRF (eg, medical history, event). Any clinically significant changes in musculoskeletal or skin

examinations throughout the study, per the investigator's opinion, should be recorded on the event CRF.

7.3.6 Physical Measurements

Height should be measured in inches without shoes. Weight should be measured in pounds without shoes.

7.3.7 Vital Signs

The following measurements must be performed: systolic/diastolic blood pressure, heart rate, respiratory rate, and temperature. Subject must be in a supine position in a rested and calm state for at least 5 minutes before blood pressure assessments are conducted. If the subject is unable to be in the supine position, the subject should be in most recumbent position possible. The position selected for a subject should be the same throughout the study and documented on the vital signs CRF. The temperature location selected for a subject should be the same throughout the study and documented on the vital signs CRF. If abnormalities are found and they are considered an adverse event, record on the event summary page.

7.3.8 Chest Radiograph

Subjects with a positive PPD test without a history of Bacillus Calmette-Guerin vaccination or subjects with a positive or indeterminate Quantiferon test will require a chest radiograph including posterior-anterior and lateral views performed within 3 months before the first dose of investigational product. The radiograph report should be read by a radiologist or per local requirement and the report must be reviewed by the investigator before enrollment of the subject.

7.3.9 Adverse Events and Serious Adverse Events

Adverse events and serious adverse events observed by the investigator or reported by the subject will be collected at all study visits.

7.3.10 Concomitant Medications

Concomitant medications are to be collected from baseline through the treatment period. For concomitant medications, collect therapy name, indication, dose, unit, frequency, route, start date and stop date. Concomitant medications include over-the-counter products and vitamins administered while the subject is on-study.

7.3.11 Injection Site Pain Score

The injection site pain score is an assessment of the severity of the subject's injection site pain and will be completed by the subject immediately after the administration of the

etanercept dose (ie, within 30 seconds) using a VAS ([Appendix D](#) [English version or [Appendix E](#) [Spanish version]]). The horizontal line is 100 mm in length with "0" and "No Pain At All" on the left end of the line and "100" and "Worst Pain Imaginable" on the right end of the line. This VAS has been specifically designed to capture injection site associated pain.

7.3.12 Physician Global Assessment of Disease Activity (PGA)

The global assessment of the subject's overall RA or PsA disease activity will be assessed by the principal investigator or sub investigator for the study by completion of a VAS. The PGA will be completed -at screening, and on day 1 and day 8 before investigational product administration. The VAS is 100 mm in length with "0" and "No Activity at All" on the left end of the line and "100" and "Worst Activity Imaginable" at the right end of the line.

7.3.13 Laboratory Assessments

All laboratory samples will be processed and sent to the central laboratory with the exception of urine pregnancy and PPD, which will be done by the site staff, and Quantiferon, which may be done by central or local laboratory. The central laboratory will be responsible for all screening and on-study serum chemistry, hematology, serum pregnancy, hepatitis C antibody, hepatitis B surface antigen and core antibody, and any other laboratory tests required. The results of this testing will be maintained in the source documents at the site. The central laboratory will provide a study manual that outlines handling, labeling, and shipping procedures for all samples. All blood samples will be obtained by venipuncture before investigational product administration. The date and time of sample collection will be recorded in the source documents at the site. Specific analytes for serum chemistry, hematology, and other testing to be conducted on blood and urine samples are listed below. Although not specifically listed, additional components, abnormal, and/or atypical cells will also be reported if present.

Table 2. Laboratory Analyte Listing

Central Lab Chemistry	Central Lab Hematology	Central Lab Other Labs	Local Lab Other Labs	Local/Central Lab Other Labs
Sodium	RBC	Hepatitis B	Urine	Tuberculosis
Potassium	RBC Morphology	surface antigen	pregnancy	testing ^b
Chloride	Hemoglobin	total		
Bicarbonate	Hematocrit	Hepatitis B core		
Total protein	Platelets	antibody		
Albumin	WBC	Hepatitis B virus		
Calcium	Differential	DNA by		
Adjusted calcium	
• Bands/stabs• Eosinophils• Basophils• Lymphocytes• Monocytes• Neutrophil ANC	polymerase		
Magnesium		chain reaction		
Phosphorus		Hepatitis C		
Glucose		antibody		
BUN or Urea		Serum beta		
Creatinine		hCG ^a		
Uric acid				
Total bilirubin				
Direct bilirubin				
Alkaline phosphatase				
AST (SGOT)				
ALT (SGPT)				

Abbreviations: ALT = alanine aminotransferase, ANC = absolute neutrophil count, AST = aspartate aminotransferase, BUN = blood urea nitrogen, hCG = human chorionic gonadotropin, PPD = purified protein derivative, RBC = red blood cell, SGOT = serum glutamic oxaloacetic transaminase, SGPT = serum glutamic-pyruvic transaminase, WBC = white blood count.

^aAll female subjects except those who are confirmed surgically sterile or at least 2 years postmenopausal or per the definition in [Section 6.8](#).

^b Subjects must receive either a PPD test or Quantiferon testing at screening.

7.3.14 Tuberculosis Testing

7.3.14.1 Purified Protein Derivative (PPD)

All subjects who have never received Bacillus Calmette-Guerin vaccination must receive a PPD test before enrollment in the study. The test must be read by a trained licensed healthcare professional 48 to 72 hours after the test material is placed intradermally under the skin. PPD test kits will not be provided by the sponsor and must be procured locally.

7.3.14.2 Quantiferon

Subjects with a positive PPD test and a history of Bacillus Calmette-Guerin vaccination will require Quantiferon testing. If testing is performed by central laboratory then refer to the central laboratory manual for instructions on sample collection, processing, and shipping of samples.

7.3.15 Urine Pregnancy Test

All females, except those who are confirmed to be of non-childbearing potential (refer to [Section 6.8](#) for this criteria), must have a negative urine pregnancy test at day 1, before administering the first dose of etanercept. Urine pregnancy tests will be performed locally at each site. The central laboratory will provide the urine pregnancy tests.

7.3.16 Hepatitis B and C Status

The following should be followed for the determination of hepatitis B and C status:

- if hepatitis B and/or hepatitis C status is known to be positive by serology no additional laboratory testing procedures are required
- if hepatitis B and/or hepatitis C status is not known to be positive by serology, the following laboratory testing is required:
 - hepatitis B surface antigen
 - if results are hepatitis B surface antigen positive, no additional testing is necessary
 - hepatitis B Core Antibody
 - if results are hepatitis B core antibody positive but negative for hepatitis B surface antigen, additional testing is necessary for hepatitis B virus DNA by polymerase chain reaction
 - hepatitis C virus antibody
- if results are hepatitis C virus antibody positive, no additional testing is necessary

8. WITHDRAWAL FROM TREATMENT, PROCEDURES, AND STUDY

8.1 Subjects' Decision to Withdraw

Subjects have the right to withdraw from the study at any time and for any reason without prejudice to their future medical care by the physician or at the institution.

Subjects can decline to continue receiving investigational product and/or other protocol-required therapies or procedures at any time during the study but continue participation in the study. If this occurs, the investigator is to discuss with the subject the appropriate processes for discontinuation from investigational product, device or other protocol-required therapies and must discuss with the subject the options for continuation of the Schedule of Assessments ([Table 1](#)) and collection of data, including endpoints, adverse events, disease related events, and device related events, as applicable. The investigator must document the change to the Schedule of Assessments ([Table 1](#)) and the level of follow-up that is agreed to by the subject (eg, in person, by telephone/mail, through family/friends, in correspondence/communication with other physicians, from review of the medical records).

Withdrawal of consent for a study means that the subject does not wish to receive further protocol-required therapies or procedures, and the subject does not wish to or is unable to continue further study participation. Subject data up to withdrawal of consent will be included in the analysis of the study, and where permitted, publically available data can be included after withdrawal of consent. The investigator is to discuss with the subject appropriate procedures for withdrawal from the study.

8.2 Investigator or Sponsor Decision to Withdraw or Terminate Subjects' Participation Prior to Study Completion

The investigator and/or sponsor can decide to withdraw a subject(s) from investigational product, device, and/or other protocol-required therapies, protocol procedures, or the study as a whole at any time before study completion.

8.3 Reasons for Removal From Treatment or Study

8.3.1 Reasons for Removal From Treatment

Reasons for removal from protocol-required investigational product(s) or procedural assessments include any of the following:

- subject request
- safety concern (eg, due to an adverse event, ineligibility determined, protocol deviation, non-compliance, requirement for alternative therapy, pregnancy)
- death
- lost to follow-up
- decision by Sponsor (other than subject request, safety concern)
- disease flare requiring treatment not allowed in the protocol (eg, colitis, asthma)

8.3.2 Reasons for Removal From Study

Reasons for removal of a subject from the study are:

- decision by sponsor
- withdrawal of consent from study
- death
- lost to follow-up

9. SAFETY DATA COLLECTION, RECORDING, AND REPORTING

9.1 Definition of Safety Events

9.1.1 Adverse Events

An adverse event is defined as any untoward medical occurrence in a clinical study subject. The event does not necessarily have a causal relationship with study treatment.

The investigator is responsible for ensuring that any adverse events observed by the investigator or reported by the subject are recorded in the subject's medical record.

The definition of adverse events includes worsening of a pre-existing medical condition. Worsening indicates that the pre-existing medical condition or underlying disease (eg, diabetes, migraine headaches, gout) has increased in severity, frequency, and/or duration more than would be expected, and/or has an association with a significantly worse outcome than expected. A pre-existing condition that has not worsened more than anticipated (ie, more than usual fluctuation of disease) during the study or involves an intervention such as elective cosmetic surgery or a medical procedure while on-study, is not considered an adverse event.

An adverse device effect is any adverse event related to the use of a medical device. Adverse device effects include adverse events resulting from insufficient or inadequate instructions for use, adverse events resulting from any malfunction of the device, or adverse events resulting from use error or from intentional misuse of the device.

The investigator's clinical judgment is used to determine whether a subject is to be removed from treatment due to an adverse event. In the event a subject requests to withdraw from protocol-required therapies or the study due to an adverse event, refer to [Section 8.1](#) for additional instructions on the procedures recommended for safe withdrawal from protocol-required therapies or the study. All adverse events will be summarized as described below based on the safety analysis set, overall, by indication, treatment arm, and by period.

9.1.2 Serious Adverse Events

A serious adverse event is defined as an adverse event that meets at least 1 of the following serious criteria:

- fatal
- life threatening (places the subject at immediate risk of death)
- requires in-patient hospitalization or prolongation of existing hospitalization
- results in persistent or significant disability/incapacity
- congenital anomaly/birth defect
- other medically important serious event

A disease related event such as worsening of symptoms of RA or PsA is to be reported as a serious adverse event if:

- the subject's pre-existing condition becomes worse than what the investigator would consider typical for a subject with the same underlying condition, or

- if the investigator believes a causal relationship exists between the investigational medicinal product(s)/protocol-required therapies and the event,
- and the event meets at least 1 of the serious criteria.

All adverse events of malignancies should be classified as serious adverse events.

An adverse event would meet the criterion of “requires hospitalization”, if the event necessitated an admission to a health care facility (eg, overnight stay).

If an investigator considers an event to be clinically important, but it does not meet any of the serious criteria, the event could be classified as a serious adverse event under the criterion of “other medically important serious event”. Examples of such events could include allergic bronchospasm, convulsions, blood dyscrasias, DILI (see [Appendix A](#) for DILI reporting criteria), or events that necessitate an emergency room visit, outpatient surgery, or urgent intervention.

9.2 Safety Event Reporting Procedures

9.2.1 Adverse Events

9.2.1.1 Reporting Procedures for Adverse Events That Do Not Meet Serious Criteria

The investigator is responsible for ensuring that all adverse events observed by the investigator or reported by the subject that occur after signing of the informed consent form through the end of treatment period are reported using the Event CRF.

The investigator must assign the following adverse event attributes:

- Adverse event diagnosis or syndrome(s), if known (if not known, signs or symptoms),
- Dates of onset and resolution (if resolved),
- Severity (and/or toxicity per protocol),
- Assessment of relatedness to etanercept and SureClick device, study procedures/study activities, and
- Action taken.

The adverse event grading scale used will be the Common Toxicity Criteria. The grading scale used in this study is described in [Appendix A](#). **If the severity of an adverse event changes from the date of onset to the date of resolution, record as a single event with the worst severity on the Event CRF.**

The investigator must assess whether the adverse event is possibly related to the etanercept and SureClick device. This relationship is indicated by a “yes” or “no” response to the question: Is there a reasonable possibility that the event may have been caused by the etanercept and SureClick device?

The investigator is responsible for reviewing laboratory test results and determining whether an abnormal value in an individual study subject represents a clinically significant change from the subject's baseline values. In general, abnormal laboratory findings without clinical significance (based on the investigator's judgment) are not to be recorded as adverse events. However, laboratory value changes that require treatment or adjustment in current therapy are considered adverse events. Where applicable, clinical sequelae (not the laboratory abnormality) are to be recorded as the adverse event.

The Investigator is expected to follow reported adverse events until stabilization or reversibility.

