3.5 Estimated Study Duration

3.5.1 Study Duration for Subjects

After signing the informed consent, subjects should be enrolled within 14 days. The planned length of participation in the study for an individual a subject is as follows:

- Up to a 14 day screening period
- 2-week treatment period
- 30 day post treatment safety follow-up

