7.1 Schedule of Assessments

Table 1. Schedule of Assessments

	Screening	Double-blind Treatment Period		Safety Follow-up/EOS
Days	-14 to -1	1 (\pm 3 days)	8 (\pm 3 days)	38 (\pm 7 days)^a
GENERAL & SAFETY ASSESSMENTS				
Informed consent	X			
Demographic data	X			
Registration via IVR/IWR	X			
Eligibility criteria	X			
Medical history	X			
Medication history	X			
Concomitant medications	X	X	X	
Adverse events ^b	X	X	X	
Serious adverse events ^b	X	X	X	X
Physical examination ^c	X	X	X	
Vital signs	X	X	X	
Weight	X			
Height	X			
Chest x-ray (if needed) ^d	X			
LABORATORY ASSESSMENTS				
Serum pregnancy test ^e	X			
Pregnancy test (urine) ^e		X		
Hematology profile	X			
Chemistry profile	X			
Tuberculosis testing ^f	X			
Hepatitis B and C serologies ^g	X			
DOSING				
Investigational product dispensation (etanercept)		X	X	
DISEASE ASSESSMENTS				
Physician global assessment of disease activity (VAS 0-100)	X	X	X	
SUBJECT ASSESSMENTS (Reported Outcomes)				
Injection site pain (VAS 0-100)		X	X	

Footnotes defined on next page.

EOS = end-of-study, IVR = interactive voice response, IWR = interactive web response, PPD = purified protein derivative, TNF = tumor necrosis factor, VAS = Visual Analog Scale

^a Thirty days (+ 7 days) after their last dose of etanercept, subjects will be contacted by phone by the study staff to follow-up on any continuing serious adverse events and inquire about the emergence of any new serious adverse events.

^b Adverse events and serious adverse events are collected from signing the informed consent form. Adverse device effects are included in the collection of adverse events. Adverse events are collected through the end of treatment period.

^c A full physical examination will be completed at the screening visit. Subsequent physical examinations will be conducted per standard of care to monitor for any changes.

^d Only for subjects with a positive tuberculosis test (ie, positive PPD or positive or indeterminate Quantiferon).

^e For all females, unless at least 2 years postmenopausal or postmenopausal status has been confirmed or history of hysterectomy, bilateral salpingectomy, or bilateral oophorectomy.

^f Subjects will receive either a PPD test or Quantiferon test at screening. National guidelines should be followed for appropriate tuberculosis screening in the setting of anti-TNF therapy.

^g Subjects positive for hepatitis B core antibody may require additional testing for hepatitis B DNA by polymerase chain reaction.

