A treatment-emergent adverse event is any adverse event that begins or worsens after the initial dose of investigational product and before the end of study. The severity of each adverse event will be graded using the CTCAE version 4.0 criteria, to be consistent with the version used for all etanercept studies. Adverse events will be coded using MedDRA (version 19.0 or later).

7. Analysis Subsets

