10.7 Safety Analyses

10.7.1 Adverse Events and Disease Related Events

The Medical Dictionary for Regulatory Activities (MedDRA) version 19.0 or later will be used to code all events categorized as adverse events (AEs) to a system organ class and a preferred term. The severity of each adverse event will be graded using CTCAE version 4.0 criteria.

The subject incidence of AEs will be summarized for all treatment-emergent AEs, serious AEs, AEs leading to withdrawal of investigational product, fatal AEs.

Subject incidence of all treatment-emergent AEs, serious AEs, AEs leading to withdrawal of investigational product, and fatal AEs will be tabulated by system organ class and preferred term in descending order of frequency.

Summaries of treatment-emergent and serious adverse events will be tabulated by system organ class, preferred term, and grade in descending order of frequency.

Adverse events (such as injection site reactions) occurring during different periods of the treatment may be examined to evaluate the safety and tolerability of a current formulation versus the modified formulation of etanercept.

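### Recording a changing adverse event once, at its worst grade, leaves the SAP unable to tell whether a screening-onset event worsened after dose 1, or in which period an event spanning both doses peaked

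*Protocol*

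**What the plan says.** **Collection.** Table 1, footnote b, of the protocol states: "Adverse events and serious adverse events are collected from signing the informed consent form". Section 9.2.1.1 likewise covers non-serious events "that occur after signing of the informed consent form through the end of treatment period are reported using the Event CRF". Section 3.5.1 allows "Up to a 14 day screening period", so an AE can be on record before any dose is given.

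**Recording.** Section 9.2.1.1 asks the investigator for the diagnosis, the onset and resolution dates, severity, relatedness and action taken. If severity changes between onset and resolution, the site must "record as a single event with the worst severity on the Event CRF". The same section adds: "The Investigator is expected to follow reported adverse events until stabilization or reversibility". The grade on the record can therefore be reached well after onset, including after dose 2.

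**Analysis.** SAP Section 6 defines a treatment-emergent AE as "any adverse event that begins or worsens after the initial dose of investigational product and before the end of study". SAP Section 10.7.1 plans: "Summaries of treatment-emergent and serious adverse events will be tabulated by system organ class, preferred term, and grade". It also says that AEs in different periods may be examined to contrast the two formulations. Protocol Section 9.1.1 is firmer and commits to summarizing all AEs by indication, by treatment arm and by period. SAP Appendix A covers partial or missing start and stop dates only.

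**The concern.** A stated recording rule discards information that a stated analysis definition uses. To apply the *worsens* limb, the analyst needs the grade before dose 1 and the date on which it rose. To place a worst grade in a period, the analyst needs to know whether it was reached before or after dose 2. Neither item is among the listed attributes.

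Without them, the programmer has to choose a convention that the SAP does not state. Going by onset date alone loses every screening-onset event that worsened on treatment. Counting every screening-onset event still ongoing at dose 1 takes in events that peaked before dosing. In a crossover with doses about 7 days apart, an AE that lasts through dose 2 raises a similar question about which formulation its worst grade belongs to.

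**Working it through.** The plan gives no figure to reproduce. The check compares what the record keeps with what the analysis needs, using hypothetical histories with dose 1 on Day 1 and dose 2 on Day 8. Worsening is read as a rise in grade.

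| History | Grade path | Stored onset and grade | Treatment-emergent under SAP Section 6? | When the worst grade occurred |
|---|---|---|---|---|
| 1 | grade 1 on Day -5, grade 2 on Day 3 | Day -5, grade 2 | yes | period 1 |
| 2 | grade 1 on Day -5, grade 2 on Day -2 | Day -5, grade 2 | no | before dosing |
| 3 | grade 1 on Day 2, grade 3 on Day 9 | Day 2, grade 3 | yes | period 2 |
| 4 | grade 1 on Day 2, grade 3 on Day 4 | Day 2, grade 3 | yes | period 1 |

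**Treatment-emergent status.** Histories 1 and 2 store the same onset and grade but have different status. With the same resolution date, the dates and grade cannot separate them. Relatedness is at most a hint: it is not a date, and a worsening judged unrelated is still treatment-emergent.

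**Period.** Histories 3 and 4 are both treatment-emergent, and grade 3 is the correct overall worst grade for each. The record does not show whether grade 3 came before or after dose 2.

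**Which records are ambiguous.**
- An AE with onset before dose 1 that resolved before dose 1 is not treatment-emergent. Taking grade 1 as the lowest grade, a record with worst grade 1 cannot have risen. The first problem is therefore confined to screening-onset AEs still ongoing at dose 1 with worst grade 2 or more.
- By the same reasoning, the second problem is confined to AEs ongoing at dose 2 with worst grade 2 or more.

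**Size per affected subject**, with the planned 112 subjects as denominator:
- Histories 1 and 2: one subject classified the other way moves overall treatment-emergent incidence by at most 1/112 = 0.9 points. If k subjects depend on such a record alone, incidence is known only to within k/112. The documents give no basis for k.
- Histories 3 and 4: overall incidence moves by 0.
- History 3, if the analyst assigned by onset: grade 3 incidence would be 1/112 = 0.9 points too high for the first formulation and 0.9 points too low for the second. For this subject's sequence, that is a shift of 2/112 = 1.8 points in the contrast. With the 2 × 53 = 106 completers that the plan expects, the figures are 1/106 = 0.9 and 2/106 = 1.9 points.

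**The case against.** Several counter-arguments have force.

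- **Worsening of a pre-existing condition is already an AE.** Protocol Section 9.1.1 says so, and such a worsening can carry its own onset date. This stands. A reader might infer that the whole worsening limb of the SAP definition is empty. It is not: the gap concerns only events first recorded as AEs between consent and dose 1. Medical history also runs through the first dose (Section 7.3.3), so a site could file a screening event either way. The protocol does not settle which, and the single-record rule points to one record.
- **Injection-site reactions are largely protected.** A reader might infer that the rule puts dose-2 injection-site reactions on the first formulation. Section 6.2.1.1 sends the second injection to the other thigh or the opposite side of the abdomen, and SAP Section 10.7.5 lists site and laterality. A reaction at the second site is naturally a new event with its own onset. What remains is mainly AEs not local to the injection site.
- **No section assigns AEs by onset.** This is correct, so misattribution to the first formulation is a possibility and not something the plan prescribes. But no assignment rule is given at all, and any rule would lack the date of the worst grade.
- **The Event CRF is not in the documents.** It may hold more fields, and source records may hold the date of worsening. No section brings such a date into the analysis data. The before-first-dose box on the contingency form is for serious events and marks onset, not worsening.
- **The rule was added deliberately in Amendment 1, and few events are involved.** Both are true. The SAP was written for that amended protocol and still uses *worsens*, so the mismatch is in the current text.

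**Conclusion.** The point holds in a limited form. From the attributes in Protocol Section 9.2.1.1, the worsening part of the SAP definition cannot be applied to AEs with onset between consent and dose 1. The worst grade of an AE ongoing across dose 2 cannot be placed in a period or formulation for the summary promised in Protocol Section 9.1.1.

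The number of affected events is probably small, because screening lasts at most 14 days and there are two single doses a week apart. The primary VAS analysis and the overall worst grade of events starting after dose 1 are not affected. The documents do not support a claim that the safety comparison as a whole is biased toward either formulation.

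The conclusion assumes that the Event CRF captures what Section 9.2.1.1 lists and no grade-change date. The rule sits in the section on non-serious AEs. Serious events also go on the Event CRF, but the protocol does not say whether the rule applies to them. The repair is worth making because a stated rule defeats a stated definition and the change is small.

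**What to change.** Keep the single-record rule, with two exceptions in the CRF completion guidance:

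1. If an AE that began before dose 1 worsens after dose 1, record the worsening as a new event linked to the first, with its own onset date, its grade and a before/after-dose mark. The mark is needed because Section 6.2.1.1 records the dose date but not the time, so a change on the day of dosing cannot be ordered by date.
2. For an AE ongoing at dose 2, record the worst grade before and the worst grade after dose 2. Alternatively, record the date of the grade increase, with the same mark if it falls on the dosing day.

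In the SAP:
- Derive treatment-emergent status from these fields. State that worsening means a grade after the dose above the worst grade before it.
- Assign an AE that spans both doses to the first period by its onset and its grade before dose 2. Assign it to the second period as well only if it worsened after dose 2.
- Count each subject once per preferred term overall and once per period.

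The cost is a few extra CRF entries, one de-duplication rule for linked records and a short SAP addition. No visit, assessment or primary analysis changes.
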